## LIST OF ABBREVIATIONS

	Advance Friend	
AE	Adverse Event	
AIC	Akaike Information Criterion	
ASL	Arterial Spin Labeling	
BBB	Blood Brain Barrier	
BHI	Breath Holding Index	
BIC	Bayesian Information Criterion	
BOLD (MRI	Blood Oxygen Level Dependent	
sequence)		
BP	Blood Pressure	
BSI	Brief Symptom Inventory	
CBF	Cerebral Blood Flow	
CC	Cubic Centimeter	
CDE	Common Data Elements	
CVR	Cerebrovascular reactivity	
cGMP	cyclic guanosine monophosphate	
CO 2	Carbon dioxide	
CVLT	California Verbal Learning Test	
DOD	Department of Defense	
DSMP	Data Safety Monitoring Plan	
DTI	Diffusion tensor imaging	
DTI-SPGR	Diffusion Tensor Imaging - Spoiled Gradient Echo	
DVI	Diffuse Vascular Injury	
DWI	Diffusion Weighted Imaging	
Et	End Tidal (CO2)	
FDA	Food and Drug Administration	
FLAIR	Fluid attenuated inversion recovery	
fMRI	Functional Magnetic Resonance Imaging	
GCP	Good Clinical Practices	
GEE	Generalized Estimating Equations	
GLP	Good Laboratory Practices	
GMP	Good Manufacturing Practices	
GRE	Gradient Echo	
HIPAA	Health Insurance Portability and Accountability Act	
ICH	International Conference on Harmonisation	
IND	Investigational New Drug	
IRB	Institutional Review Board	
ML	Milliliters	
MR	Magnetic Resonance	
MRI	Magnetic Resonance Imaging	
MPRAGE	Magnetization Prepared Rapid Gradient Echo	
mTBI	Mild Traumatic Brain Injury	
NAION	Non-arteritic Anterior Ischemic Optic Neuropathy	
NIH	National Institutes of Health	
NIH CC	National Institutes of Health Clinical Center	
NINDS	National Institutes of Neurological Disease and Stroke	
NO	Nitric Oxide	
NOS	Nitric Oxide Synthase	
PDE5	Phosphodiesterase 5 (inhibitors)	
PI	Principal Investigator	
QC	Quality Control	
REDCap	Research Electronic Data Capture	

Sildenafil Treatment for Chronic Traumatic Microvascular Injuries

#### Protocol UT-7529

rfcMRI	Resting state functional connectivity MRI
SAE	Serious Adverse Event
Sildenafil	Viagra®
SWI	Succeptability Weighted Imaging
SWLS	Satisfaction with Life Scale
TBI	Traumatic Brain Injury
TCVI	Traumatic Cerebral Vascular Injury
TCD	Transcranial Doppler
TMT	Trail Making Tests
TTP	Time to Peak
UTSWMC	University of Texas Southwestern Medical Center
WAIS-IV	Wechsler Adult Intelligence Scale
WRAT	Wide Range Achievement Test

Table 1. List of Abbreviations.

	matter degeneration (3-13). Recently, use of magnetic resonance imaging (MRI)-Blood Oxygen Level Dependent (BOLD) combined with hypercapnia (high spatial and temporal resolution) by our research group has proven to be more sensitive at measuring alterations of cerebral blood flow (CBF) in TBI subjects. The goal of our proposed research is to test the efficacy of Viagra® (sildenafil) at normalizing CBF and improving cognitive outcomes in people that have experienced a TBI. Sildenafil is a phosphodiesterase-5 (PDE- 5) inhibitor that has previously been administered as a therapy for high blood pressure and erectile dysfunction (14, 15). In people that have been affected by stroke-induce neurotrauma, sildenafil improved CBF and was found to be neuroprotective (16-21). With respect to chronic TBI, our preliminary data demonstrates that sildenafil therapy potentiates cardiovascular reactivity (CVR) in areas of the brain with damaged endothelium. In this proposal, we will test the hypothesis that sildenafil treatment in boxers/MMA fighters soon after concussion normalizes CBF, potentiates CVR, reduces post-concussion symptoms, and improves cognition.
Objectives:	
 
Objective 1: To demonstrate that administration of the vasodilator, sildenafil, to concussed boxers/MMA fighters will improve/normalize various vascular properties.
 
Objective 2: We will determine if sildenafil reduces symptoms and improves cognition in the athletes.
 

Endpoint	The primary outcome measures will be global CVR to hypercapnia, reduced symptoms, improved cognition in concussed athletes treated with a single or multiple doses of sildenafil (60mg). In the secondary outcome measure, we assess sildenafil (60mg) therapy reduces the levels of fluid-based biomarkers of injury.
Population:	The study population for this protocol consists of 100 boxers between the ages of 18 and 35 (both men and women) who have suffered a concussion. The athletes will be recruited from fitness centers within the North Texas area. Testing will occur at UT Southwestern Medical Center, Dallas, Texas. The study will be comprised of the experimental (boxers/MMA fighters) and age- matched non-boxer, healthy controls.
Phase:	2
Number of Sites enrolling participants:	1

STU032018-063, [name], FormA-ResearchProtocol, Mod\_6, 11-25-19 (1) NIH-FDA Clinical Trial Protocol

**Description of Study** Agent : Sildenafil is a phosphodiesterase-5 (PDE-5) inhibitor that has previously been administered as a therapy for high blood pressure and erectile dysfunction. Sildenafil (60mg) will be administered at various time-points to the athletes to assess efficacy and tolerability.

[figure not shown]
Study	Duration:	3 Years
Juuy	Duration.	5 1 6 4 3

Protocol UT-7529

Participant Duration: 30 Days

## SCHEMATIC OF STUDY DESIGN

Figure 1. Sildenafil Pilot Study.

# 2 INTRODUCTION: BACKGROUND INFORMATION AND SCIENTIFIC RATIONALE

## 2.1 BACKGROUND INFORMATION

Traumatic Brain Injury (TBI). Each year in the United States, about 235,000 persons are hospitalized for TBI, of which approximately 50,000 die. The cost of TBI each year is approximately \$77 billion in the U.S. (Injury Prevention and Control: Traumatic Brain Injury; <www.cdc.gov/traumaticbraininjury/statistics.html>). Despite advances in neurosurgical interventions and acute monitoring, many survivors do not fully recover and are left with permanent disability (1, 2, 22, 23). Secondary brain damage which is caused by oxidant injury. inflammation, and vascular injury, may begin almost immediately after the primary injury. Even those with mild TBI may have prolonged neurological deficits, with about 15% having disabling persisting symptoms. 43% of those hospitalized for TBI have long-term disability (24-26). Consequently, chronic secondary brain injury is difficult to manage and the administration of neuroprotective agents in a chronic fashion is warranted to assist in the recovery process and decrease neuro-degeneration in this population. Multiple studies that aimed to treat mild TBI acutely with various interventions showed poor results (27). These limited findings may be due to insufficient treatment times, ineffective therapies, or lack of endophenotype data. Endophenotype guided therapies are ideal and may yield drug therapies that reduce secondary brain injury and improve outcomes within the TBI population.

**Vascular Injury and TBI.** Traumatic cerebral vascular injury (TCVI) is a debilitating TBI endophenotype. In both animal and human TBI models, TCVI results in vasodilatory deficits and other microcirculatory problems. In these models, the response to vasodilators such as nitric oxide (NO) was reduced significantly. Also, these deficits were a result of damage to the endothelium, a reduction of capillary density, intravascular microthrombi, and white-matter degeneration, resulting in motor and cognitive deficits (3-13, 28).

Following TCVI, cerebral blood flow (CBF) is affected in TBI subjects as indicated by hypo-perfusion in numerous brain structures. For example, CBF has been found to be reduced significantly in people who have experienced a severe TBI, resulting in poor long-term cognitive and functional outcomes (29-32). Also, CVR is decreased after TBI and correlates with reduced CBF, cognitive deficits, and heightened symptoms (33, 34). Other studies have demonstrated that at chronic time-points, the CBF remained abnormal in athletes even though they showed improvements with cognitive scoring and reduced symptoms at later time-points (35-38). Imaging diagnostics have proven to be vital in detecting TCVI in both symptomatic and

asymptomatic TBI subjects and should be utilized to monitor disease progression and efficacy of various treatments.

Imaging tools such as transcranial doppler (TCD) and near infra-red spectroscopy (NIRS) have been shown to measure vasospasms and CVR abnormalities in TBI survivors. A major limitation of TCD and NIRS is their lack of sensitivity, which has been demonstrated in a number of research studies (39-45), warranting the use of a more sensitive approach for identifying CBF and CVR abnormalities. Utilization of magnetic resonance imaging (MRI)-Blood Oxygen Level Dependent (BOLD) combined with hypercapnia (high spatial and temporal resolution) by our group and others has proven to be more effective in determining the hemodynamic response in TBI subjects (46-48). In control and injured people, MRI-BOLD measures the transition rate of oxygenated hemoglobin to deoxygenated hemoglobin and defines the regional/global CBF in the brain (49). Recently, preliminary data generated by our research group has proven that CBF and CVR are decreased in people with a history of TBI. The primary goal of this study is test whether sildenafil improves global CBF/CVR, reduces symptoms, and improves cognition in concussed athletes.

**Sildenafil Therapy to Improve CBF and CVR.** Sildenafil is a vasodilator that inhibits the cGMP-specific phosphodiesterase type 5 enzyme, resulting in decreased degradation of cGMP. The original use of this drug was to treat hypertension and later for erectile dysfunction (50-52). This drug is relatively safe and has been shown to increase CVR in a number of studies (53, 54). For example, in 28 patients randomized to either placebo or sildenafil, an increase in CVR was observed as early as 1 hour after administration (54). In another study, utilization of TCD showed that a single 50mg dose of sildenafil in patients with vertebra-basilar insufficiency displayed a significant increase in the diameter, area, and flow volume of the vertebral artery (55). In contrast, in healthy individuals, no effect on CBF was observed when treated with sildenafil (56, 57). Preliminary data generated by our research group demonstrates that sildenafil is efficacious at normalizing CBF and increasing CVR in TBI patients. Given the paucity of studies testing the effect of sildenafil on CBF/CVR, in this novel study, we plan to test the hypothesis that sildenafil normalizes global CBF and potentiates CVR in concussed professional boxers.

## 2.2 RATIONALE

Since we have the capability to obtain baseline (prefight) data, this population is an ideal group to study the efficacy of sildenafil at normalizing CBF, potentiating CVR, improving cognition and symptoms. The use of sildenafil is based on published reports in stroke models and preliminary data generated from our research group in TBI subjects. After suffering a concussion, we believe that this compound will effectively diminish the secondary injury in the brain and mitigate symptoms and cognitive deficits. Also, this therapy has proven to be safe in people suffering from TBI.

## 2.3 POTENTIAL RISKS AND BENEFITS

## 2.3.1 KNOWN POTENTIAL RISKS

STU032018-063, [name], FormA-ResearchProtocol, Mod\_6, 11-25-19 (1) NIH-FDA Clinical Trial Protocol

**Sildenafil:** There is a serious risk in subjects with pre-existing cardiovascular disease, hypotension (BP <90/50)/hypertension (BP> 170/110), coronary heart disease, subjects with retinitis pigmentosa there is cardiac risk.

**MRI:** Subjects are at risk for injury from the MRI magnet (3 Tesla) if they have pacemakers or other implanted electrical devices, brain stimulators, some types of dental implants, aneurysm clips (metal clips on the wall of a large artery), metallic prostheses (including metal pins and rods, heart valves, and cochlear implants), permanent eyeliner, implanted delivery pump, or shrapnel fragments. Welders and metal workers are also at risk for injury because of possible small metal fragments in the eye of which they may be unaware. Volunteers will be screened for these conditions before having an MRI, and if any are present, the MRI scan will not be performed. Volunteers will be asked specifically about metal objects being present in their body. If it is unknown whether metal is present and or if there is any question, MRI will not be performed.

Subjects with fear of confined spaces may become anxious during an MRI. Those with back problems may have back pain or discomfort from lying in the scanner. The noise from the scanner is loud enough to damage hearing, especially in people who already have hearing loss.

**Neuropsychological Testing:** There are no expected risks for the participants answering the questions. Possible adverse events may include psychological stress.

**Blood/Saliva collection:** The risk of bruising or infection are the main risks involved with the blood collection procedures. There are no known risks of providing a saliva specimen.

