## 5.2 PARTICIPANT EXCLUSION CRITERIA

- 1. Contraindication to sildenafil which includes the following:
  - a. Current use of organic nitrate vasodilators
  - b. Use of ritonavir (HIV-protease inhibitor)
  - c. Current use of erythromycin, ketoconazole, or itraconazole

STU032018-063, [name], FormA-ResearchProtocol, Mod\_6, 11-25-19 (1) NIH-FDA Clinical Trial Protocol

- d. Current use of cimetidine
- e. Current resting hypotension (BP < 90/50 mm Hg)
- f. Current severe renal insufficiency (Creatinine Clearance < 30mL/min)
- g. Current hepatic cirrhosis
- h. Current cardiac failure or coronary artery disease causing unstable angina
- i. Retinitis pigmentosa
- j. Known hypersensitivity or allergy to sildenafil of any of its components
- 2. Daily therapy with a PDE5 inhibitor within the past 2 months
- 3. Immediate hospitalization for severe concussion
- 4. History of neurological or psychiatric disorder not related to TBI
- 5. Known inclusion in another interventional clinical trial
- 6. Subjects with metal implants that would interfere with the MR imaging procedures
- 7. Sickle cell disease
- 8. History of priapism

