## 7.3.2 ENROLLMENT/BASELINE/FOLLOW-UP

#### Sildenafil Study:

#### Baseline Visit (Visit 1, Day 0)

- Obtain informed consent of potential participant verified by signature on study informed consent form
- Verify inclusion/exclusion criteria
- Obtain demographic information, medical history, head injury history, medication history, alcohol and tobacco use history
- Record vital signs, results of examinations, other assessments.
- Baseline symptom questionnaire
- Collect blood/saliva for biochemistry, biomarker testing
- MRI procedures
- Neuropsychological testing
- •

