#### Table 6. Post-Marketing Experiences Reported in Temporal Association with the use of Viagra.

Occurred predominantly in patients who had preexisting cardiovascular risk factors. Undetermined if these events are related directly to Viagra, to sexual activity, to the patient's underlying conditions, or to a combination of these factors.

Cardiovascular and Cerebrovascular	Myocardial infarction, sudden cardiac death, ventricular arrhythmia, cerebrovascular hemorrhage, transient ischemic attack, hypertension, subarachnoid and intracerebral hemorrhages, and pulmonary hemorrhage					
Special Senses	Sudden decrease or loss of hearing					
Other Events	Nervous Seizure, seizure recurrence, anxiety, and transient global amnesia					
	Urogenital	Prolonged erection, priapism, and hematuria.				
	Special Senses	Diplopia, temporary vision loss/decreased vision, ocula redness, ocular burning, ocular swelling, increased intraocular pressure, retinal vascular disease, vitreous detachment/traction, paramacular edema, and epistax				
	Non-arteritic anterior ischemic optic neuropathy (NAION)	Decreased vision including permanent loss of vision. NAION reported rarely post-marketing in temporal association with use of Viagra mostly in patients with risk factors including: Low cup to disc ratio, age over 50, diabetes, hypertension, coronary heart disease, hyperlipidemia, and smoking.				

 Table 7. Incidence of Clinical Worsening and Most Frequent Adverse Events in Daily Dosing of

 Sildenafil and Placebo (dose listed was administered 3 times each day for 12 weeks)

Sildenafil Treatment for Chronic Traumatic Microvascular Injuries

Protocol UT-7529

Dose	Placebo		Sildenafil		
	Placebo				
Number of Subjects		20mg TID	40mg TID	80mg TID	
(percent Female)	n=70 (81%)	n=69 (71%)	n=67 (70%	n=71 (79%)	
Clinical worsening	7 (10%)	3 (4%)	2 (3%)	5 (7%)	
Death	1 (1%)	0	1 (1%)	2 (3%)	
Hospitalization for pulmonary	7 (10%)	2 (3%)	2 (3%)	2 (3%)	
arterial hypertension					
Initiation of prostacyclin	1 (1)	0	0	0	
Initiation of bosentan	0	0	1 (1)	0	
Adverse Events	Placebo	Sildenafil			
		20mg TID	40mg TID	80mg TID	
Headache	27 (39%)	32 (46%)	28 (42%)	35 (49%)	
Flushing	3 (4%)	7 (10%)	6 (9%)	11 (15%)	
Dyspepsia	5 (7%)	9 (13%)	6 (9%)	9 (13%)	
Back pain	8 (11%)	9 (13%)	9 (13%)	9 (8%)	
Diarrhea	4 (6%)	6 (9%)	8 (12%)	7 (10%)	
Limb pain	4 (6%)	5 (7%)	10 (15%)	6 (8%)	
Myalgia	3 (4%)	5 (7%)	4 (6%)	10 (14%)	
Cough	4 (6%)	5 (7%)	3 (4%)	6 (8%)	
Epistasis	1 (1%)	6 (9%)	5 (7%)	3 (4%)	

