Pyrexia	2 (3%)	4 (6%)	2 (3%)	7 (10%)	
Insomnia	1 (1%)	5 (7%)	4 (6%)	3 (4%)	
Influenza	2 (3%)	4 (6%)	4 (6%)	3 (4%)	
Visual disturbance	0	0	3 (4%)	5 (7%)	
Gastritis	0	2 (3%)	2 (3%)	3 (4%)	

**FDA WARNING**: There is a potential for cardiac risk of sexual activity in patients with preexisting cardiovascular disease. Therefore, treatments for erectile dysfunction, including VIAGRA, should not be generally used in men for whom sexual activity is inadvisable because of their underlying cardiovascular status. We expect this will be rare in our study, which will not enroll subjects older than 50 years of age. Participants with hypotension, cardiac failure, or coronary artery disease with unstable angina are excluded from this study.

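### Resting blood pressure above 170/110 is named as a serious sildenafil risk in section 2.3.1, but only the low blood-pressure range is an exclusion in section 5.2

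*Combined protocol and SAP*

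**What the plan says.** The sildenafil paragraph of section 2.3.1 lists conditions in which the drug carries serious risk. Among them is "hypotension (BP <90/50)/hypertension (BP> 170/110", the only entry with numeric limits.

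Section 5.2 opens its first exclusion with "Contraindication to sildenafil which includes the following" and then gives items a to j. Item 1e is "Current resting hypotension (BP < 90/50 mm Hg". Item 1h is "Current cardiac failure or coronary artery disease causing unstable angina". Neither the rest of item 1 nor items 2 to 8 name hypertension or set an upper blood-pressure limit.

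In section 8.2.2, the FDA warning that follows the adverse-event tables ends: "Participants with hypotension, cardiac failure, or coronary artery disease with unstable angina are excluded from this study". Hypertension is absent there too.

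At the baseline visit (section 7.3.2) staff verify the inclusion and exclusion criteria and "Record vital signs, results of examinations, other assessments". No threshold or action is attached to the readings.

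**The concern.** The protocol puts the low and high ranges side by side as serious risks and gives each a figure. One figure became an exclusion and the other did not. Whether to dose someone above 170/110 is therefore left to whoever is screening that day, while the low range has a fixed limit.

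This is a participant-safety matter. It does not affect the estimand or the analysis. Section 2.3.2 says participants should expect no direct benefit, so there is little room for avoidable risk. Healthy controls are also randomized to drug or placebo (section 4.1), and they would carry the risk with no injury to treat. Table 6 says of the post-marketing events: "Occurred predominantly in patients who had preexisting cardiovascular risk factors". Its list of risk factors for the optic neuropathy NAION includes "diabetes, hypertension, coronary heart disease, hyperlipidemia, and smoking". The table leaves causality undetermined, and it gives no blood-pressure threshold.

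**Working it through.** The check is a comparison of text; the plan gives no figure on this point to reproduce.

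**Step 1: conditions named in 2.3.1 against the exclusions in 5.2**

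| Condition in 2.3.1 | Counterpart in 5.2 |
|---|---|
| Pre-existing cardiovascular disease | Narrower: cardiac failure (1h) |
| Hypotension, below 90/50 | In full (1e) |
| Hypertension, above 170/110 | None |
| Coronary heart disease | Narrower: only if causing unstable angina (1h) |
| Retinitis pigmentosa | In full (1i) |

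Two carry over in full, two in narrower form and one not at all. The mapping of cardiovascular disease to item 1h is a matter of reading. The blood-pressure rows are not: of two numeric limits, one is carried over.

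**Step 2: whether another section supplies the missing limit**

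- 5.1, inclusion: no blood-pressure criterion. Controls qualify by age, no contact sports and a negative screen for mild brain injury.
- 6.1.7, dose changes and delays: marked not applicable, so there is no rule for holding a dose.
- 7.3.1, screening: medical and concussion history are reviewed; no blood-pressure limit.
- 7.3.2, Visit 1: vital signs recorded, no threshold. Visit 2, dosing 2 hours after injury: no vital signs listed.
- 7.5.1, precautions: a caution about added effect with antihypertensive drugs, not a limit on the participant's own pressure.
- 10.1: eligibility rests on the defined inclusion and exclusion criteria, so a condition left off the list is not a defined ground for exclusion.
- 10.2.1, post-bout re-screen: symptoms or number of blows only.

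No section closes the gap. Sections 5.1 and 5.2 are shown in full, so removed text does not explain it.

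**Step 3: how many people receive the drug**

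Inputs: 100 athletes and 80 controls (section 4.1), 1:1 allocation, and 110 to 120 boxers if enrollment follows section 10.2.1.

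- Planned: (100 + 80) / 2 = 90, made up of 50 athletes and 40 controls.
- With 110 boxers: (110 + 80) / 2 = 95.
- With 120 boxers: (120 + 80) / 2 = 100.

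These count everyone on sildenafil, not those above the limit. The documents give no prevalence, and none is assumed here.

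**Step 4: room for extra screen failures among athletes**

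With 130 screened (section 4.1):

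- 100 enrolled: 130 − 100 = 30, and 30/130 = 23.1%.
- 110 enrolled: 130 − 110 = 20, and 20/130 = 15.4%.
- 120 enrolled: 130 − 120 = 10, and 10/130 = 7.7%.

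This room is not reserved for blood pressure; boxers who fail the post-bout re-screen may use it as well. For controls no number to be screened is stated.

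**The case against.** The best defense is that the plan already allows such a person to be kept out. The first exclusion is open-ended ("Contraindication to sildenafil which includes the following"), section 2.3.1 supplies the number, and Visit 1 pairs vital signs with the eligibility check. Controls are described as healthy. Sections 5.4.1 and 5.5 let investigators and medical monitors remove anyone. Nor is 5.2 the complete list of exclusions: section 8.4.2 calls pregnancy an exclusion, and 5.2 does not mention it. All of that is true, and it makes enrollment of a severely hypertensive person less likely. But for pregnancy another section states the exclusion, and for hypertension none does. Section 2.3.1 calls it a risk, not a contraindication, and the removal powers have no blood-pressure trigger. Judgment is available; a pre-dose rule is not.

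Three criticisms of the supporting evidence stand. The sentence in 8.2.2 only repeats items 1e and 1h and omits other exclusions as well, so it is not independent evidence of a gap. Table 6 supports neither the 170/110 figure nor singling out hypertension, since diabetes, hyperlipidemia and smoking appear beside it and are not excluded either. And 2.3.1 is a risk disclosure that the sponsor did not copy item by item into 5.2. The case therefore rests on 2.3.1 against 5.2.

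It could also be argued that a drug first used for hypertension (section 2.1) poses little hazard at high pressure. If that is the sponsor's view, the sentence in 2.3.1 needs correcting. Either way the two sections do not match.

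**Conclusion.** The concern holds. Under the criteria as written, a person with resting pressure above 170/110 at Visit 1 may be randomized and dosed, although the protocol itself calls that range a serious risk. About 90 people are planned to receive sildenafil (95 to 100 under the larger enrollment), but only those above the limit are affected. Their number is unknown and probably small at ages 18 to 35; that is a judgment, not a figure from the documents. The mismatch is certain from the text, while its practical consequence is not quantified. It should be corrected because the correction is cheap and concerns safety, including that of healthy volunteers.

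**What to change.** Add to exclusion 1 in section 5.2: *Current resting hypertension (BP > 170/110 mm Hg)*, applied to athletes and controls using the Visit 1 vital signs. Add hypertension to the sentence in section 8.2.2 that restates the exclusions.

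The cost is one exclusion line, one wording edit and IRB approval of the amendment (section 13.2). No new procedure is needed, because Visit 1 already records vital signs and verifies eligibility. The downside is probably a few extra screen failures; each excluded control would need a replacement.

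For athletes this change screens only the pre-fight reading. Someone below the limit then and above it 2 hours after injury would still be dosed. Closing that further gap would take a blood-pressure check at Visit 2 before the dose, which would be an added procedure.
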